#### 5.2.2. Arm 2: Crenolanib plus 5-azacitidine

#### **ARM 2 Dosing Schedule:**

- 5-azacitidine 75 mg/m² will be administered subcutaneously (SQ) or intravenously (IV) at 75 mg/m²/d for 7 days of every cycle (Days 1-7). The choice of SQ or IV administration will be selected by the treating physician and can be switched from one to another throughout the therapy as both SQ and IV forms of administration are FDA approved and considered interchangeable.
- Crenolanib will be given Days 1-28 (crenolanib will be given continuously unless toxicity occurs)

Cycles will be defined as 28 days. Patient may continue on combination crenolanib + 5-azacytidine per physician's discretion or until transplant, progression of disease, withdrawal, unacceptable toxicity, etc. (per Section 6.5).

If a patient achieves a CR/CRi/CRp, he/she will be eligible for maintenance therapy with single agent crenolanib (per physician's discretion). Crenolanib, in the maintenance setting, may be given for up to 365 days per physician's discretion.

If a patient is to receive transplant, he/she must be discontinued from study treatment prior to transplant. If at any time during maintenance a patient relapses or is taken off study for any other reason (such as transplant), an end of treatment visit is strongly recommended. This visit will occur within 30 days of discontinuing crenolanib and prior to new treatment regimen or transplant. At the end of the study, patient's survival status will be assessed.

### **5.2.3.** General Principles for Both Arms

For arms 1 and 2, patients should be given prophylactic anti-emetics from the time of enrollment to be taken prior to each dose of crenolanib and as needed as per ASCO guidelines for moderately emetogenic therapy. Oral HT3 antagonists such as ondansetron are quite effective in mitigating crenolanib associated nausea. Prophylactic antiemetic administration may be adjusted (including discontinuation of prophylactic antiemetics as appropriate) throughout the course of therapy as needed to minimize and manage nausea and/or vomiting.

The following bullet points are exceptions allowed following discussion with and approval by the sponsor and PI.

- Cycles may be started early (but not earlier than cycle day 21) for patients with active disease if judged in the best interest of the patient by the treating physician and PI.
- Subsequent cycles may be delayed for recovery of toxicity. Delays in start of subsequent cycles greater than 7 weeks will be acceptable only for patients who are deriving clinical benefit and after discussion with the principal investigator of potential risk/benefit ratio.
- Crenolanib therapy may continue even if there is a delay in the start of azacitidine or standard salvage chemotherapy provided the delay is not due to toxicity possibly related to crenolanib.

#### 5.3. Study Conduct and Definitions of DLT and MTD

#### **5.3.1. Definition of DLT**

DLT is defined as any clinically significant adverse event or abnormal laboratory value occurring during the first cycle of therapy that is not related to concomitant medications, co-morbidities or underlying disease (leukemia), and that is not expected for the chemotherapy being used together with crenolanib.

- Non-hematologic DLT is defined as any grade 3 or 4 non-hematologic toxicities despite optimal supportive care. For example, grade 3 or 4 nausea, vomiting, or diarrhea that cannot be controlled with standard antiemetic or antidiarrheal medications used at optimal dose within 72 hours of onset are considered DLTs.
  - Tumor lysis syndrome is considered DLT. If 2 out of the 10 first patients are observed to experience the tumor lysis syndrome of Grade 4, the trial will be put on hold and a mitigation strategy will be implemented.
- Hematologic DLT is defined as grade ≥3 neutropenia and/or thrombocytopenia with a hypocellular bone marrow lasting for 6 weeks or more after the last dose of therapy in the absence of residual leukemia (i.e., with less than 5% blasts).
  - o Anemia will not be considered for the definition of DLT.

#### 5.3.2. Cohort Management

Patients will be treated in cohorts of 6 patients at each dose level starting at dose level 1 of 60 mg TID for each Arm.

- If DLT occurs in ≥2/6 patients at dose level 1 (60 mg TID), this dose level would exceed the MTD, and a dose level 0 (60 mg BID) will be used. If 0-1/6 patients experience DLT, an additional 6 patients will be enrolled at dose level 2 (80 mg TID).
- Patients who are removed from study before cycle 1 day 28 for any reason other than toxicity and have not experienced DLT will be replaced.
- DLT and MTD will be established independently for each treatment arm (i.e. arm 1: crenolanib + standard salvage chemotherapy and arm 2: crenolanib + AZA).
- For arm 1: One induction cycle can continue for a minimum of 28 days and a maximum of 60 days from the start of induction chemotherapy, until the start of the second cycle of therapy (reinduction or consolidation) or achievement of CR/CRi/CRp. For arm 2: One cycle of crenolanib therapy is defined as 28 days from the first ingestion of study drug.

- During maintenance, one cycle of therapy is defined as 28 consecutive days of crenolanib therapy.
- Counting cycle days: If study drug is held or a dose is missed the missed/held dose should not be made up. Dosing will resume with the next scheduled dose. The patient should enter in his/her patient dosing diary the doses missed. If drug is held for one or more days, the counting of cycle days should continue as if uninterrupted. The start of cycle 1 is denoted by the start of chemotherapy. The scheduled procedures/visits should comply with the study calendar regardless of amount of study drug administered in a cycle.
- For arm 1: If myelosuppression persists more than 60 days from the day of the last dose of therapy with evidence of a hypocellular marrow (marrow cellularity less than 5%) without evidence of leukemia, standard salvage chemotherapy will be discontinued. Crenolanib might be continued or re-initiated in patients deriving benefit after discussion with the PI and the sponsor.
- For arm 2: If myelosuppression persists more than 60 days with evidence of a hypocellular marrow (marrow cellularity less than 5%) without evidence of leukemia is observed subsequent courses of Azacitidine may be given at the next lower dose. If the peripheral counts do not recover (ANC <1 x10^9/L and/or platelets <30 x10^9/L) but there is evidence of residual leukemia in the bone marrow, subsequent cycles can be administered at the discretion of the treating physician not earlier than 3 weeks (21 days) after the prior cycle.
- If the peripheral counts do not recover (ANC  $< 1 \times 10^9$ /L and/or platelets  $< 30 \times 10^9$ /L) but there is evidence of residual leukemia in the bone marrow after cycle 1, subsequent cycles of Azacitidine or standard salvage chemotherapy can be administered at the discretion of the treating physician (following discussion with the sponsor and PI) not earlier than 3 weeks (21 days) after the start of the prior cycle.
- For patients who discontinue therapy, the reason for treatment discontinuation will be captured.
- Patients who experience crenolanib-specific (defined as determined by the principal investigator) grade 3-4 extramedullary toxicities during induction cycle 1, and who are not in CR after cycle 1, may receive a second induction course at -1 dose level with respect to crenolanib (as defined in table above).
- Other dose modification schedules felt to be in the best interest of the patient may be permitted, after discussion with the principal investigator.
- If judged more beneficial for patient care and disease control, patients may have dose reductions to allow for continuation of therapy with acceptable myelosuppression.
- The dose of chemotherapy treatment in subsequent courses will be reduced by 25% for grade 3-4 extramedullary toxicities, or for severe life-threatening infections.
- In responding patients, courses will be given at 4 to 6 week intervals provided the granulocyte count has recovered to  $>1.0 \times 10^9 / L$  and the platelet count to  $>50 \times 10^9 / L$ . In patients with persistent disease, therapy could be restarted once counts recover to the pretreatment values.
- Dose adjustments for only one of the drugs can be made if, in the opinion of the treating physician, the toxicity is attributable to one of the drugs.

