#### 5.2. Treatment Schedule

Crenolanib will be administered for the phase 1 portion as described according to dose levels in Table 6.2. The starting dose is 60 mg TID (dose level 1). Dose escalations will proceed to 80 mg TID (dose level 2) and 100 mg TID (dose level 3) based on DLTs. DLTs will be evaluated during the first cycle of crenolanib treatment. Patients who experience crenolanib related DLTs at dose level 1 will receive a dose reduction to dose level 0 (60 mg BID). Patients who encounter DLTs at dose levels 2 and 3 will receive dose reduction at 1 dose level lower.

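### The plan sets no minimum crenolanib exposure for counting a phase I patient as without DLT, and its replacement rules and DLT window do not agree

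*Combined protocol and SAP*

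**What the plan says.** **Clearing rule.** Under Section 5.3.2, 0 or 1 DLT in six patients opens the next dose level. Table 5.1 sorts patients into those with a DLT, those without, and those with data pending. It does not say when a pending patient becomes one without a DLT.

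**Replacement.** Section 5.3.2 replaces "Patients who are removed from study before cycle 1 day 28 for any reason other than toxicity", provided no DLT has occurred. Section 5.5 has a second rule, placed next to the definition of an adequate efficacy trial: a patient who does not complete one crenolanib cycle is replaced, except where the cause is toxicity or progressive disease.

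**Clock.** Section 5.3.2: "The start of cycle 1 is denoted by the start of chemotherapy", and "If drug is held for one or more days, the counting of cycle days should continue as if uninterrupted". The Arm 1 definition reads "One induction cycle can continue for a minimum of 28 days and a maximum of 60 days from the start of induction chemotherapy". The Arm 2 definition reads "One cycle of crenolanib therapy is defined as 28 days from the first ingestion of study drug".

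**DLT window.** Sections 5.1 and 5.3.1 use the first cycle of treatment or therapy. Section 5.2 says "DLTs will be evaluated during the first cycle of crenolanib treatment", and Section 3 says the same.

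**Evaluability.** The synopsis asks only for 28 days on study. Section 5.5 makes anyone with a single dose evaluable for toxicity. No section gives a minimum number of crenolanib doses or days for the escalation decision.

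**The concern.** A DLT count out of six says something about a dose only if the six patients took that dose for long enough. If a patient with little crenolanib exposure stays in the denominator, the observed DLT count tends to be lower than the dose would produce under full exposure, and the dose clears more easily. The patient of most interest is the one who could not keep taking crenolanib because of toxicity short of a DLT. That patient is informative about tolerability, yet enters the count as a success for the dose.

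Arm 1 adds a second route. Crenolanib starts several days after chemotherapy, so part of the interval to day 28 has no crenolanib in it. Any error carries forward, because Section 12.1 moves the six patients treated at the MTD into phase II.

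**Working it through.** **1. The plan's own figure.** The documents give no operating characteristics for phase I. The one figure tied to the rule is the maximum of 18 patients per arm (Section 12.4): 3 dose levels × 6 = 18, which reproduces.

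**2. The two replacement rules side by side, for a patient without a DLT.**

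| Patient | Section 5.3.2 | Section 5.5 |
|---|---|---|
| Leaves before day 28 for progression | replaced | not replaced |
| Leaves before day 28 for toxicity below DLT | not replaced | not replaced |
| Stays on study, crenolanib stopped early for a reason other than toxicity or progression | not replaced | replaced |
| Stays on study, crenolanib held for persistent grade 2 toxicity (a hold allowed by Table 6.1) | not replaced | not replaced |

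In the last row the patient has not left the study, so Section 5.3.2 does not apply. Under Section 5.5 either the cycle counts as completed, because days run on during a hold, or the toxicity exception applies. Non-hematologic DLT requires grade 3 or 4 (Section 5.3.1), so the event is not a DLT.

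**3. Crenolanib days in Arm 1 by cycle 1 day 28, with no holds.** Start days are from Section 5.2.1, each with a +3 day window. Days to day 28 = 28 − start + 1. If the next cycle begins on day 29 after the 72-hour stop, the last crenolanib day is 25, so days = 25 − start + 1.

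| Regimen | Start day | Days by day 28 | Days if next cycle starts day 29 |
|---|---|---|---|
| Idarubicin/cytarabine | 5 to 8 | 24 to 21 | 21 to 18 |
| FLAG-Ida | 6 to 9 | 23 to 20 | 20 to 17 |
| MEC | 8 to 11 | 21 to 18 | 18 to 15 |

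The range by day 28 is 18 to 24 days, or 64% to 86% of 28. Arm 2 has no lag, so only holds and missed or vomited doses reduce exposure there.

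**4. Illustration of the effect on clearing a dose.** Assumptions, not document figures: a DLT probability p over 28 crenolanib days, and a constant hazard over crenolanib days. Then

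- DLT probability over d days: p_d = 1 − (1 − p)^(d/28)
- Chance of clearing: P(at most 1 of 6) = (1 − p_d)^6 + 6 p_d (1 − p_d)^5

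For p = 30% and d = 18, p_d = 1 − 0.70^(18/28) = 0.205, and the chance is 0.795^6 + 6 × 0.205 × 0.795^5 = 0.643. With d = 28 it is 0.70^6 + 6 × 0.30 × 0.70^5 = 0.420.

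| Assumed 28-day DLT rate | 28 days | 21 days | 18 days | 15 days |
|---|---|---|---|---|
| 20% | 66% | 77% | 81% | 86% |
| 30% | 42% | 57% | 64% | 72% |
| 40% | 23% | 38% | 47% | 56% |

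Each column gives all six patients the same exposure. The 15-day column combines the latest MEC start with a next cycle on day 29, so it is an extreme.

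**The case against.** Several stronger readings are tempting, and the documents do not support them.

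- **That a patient is declared DLT-free at day 28.** No section says so. Day 28 is a replacement cut-off. The DLT period is the whole first cycle, up to 60 days in Arm 1, and hematologic DLT needs 6 weeks or more after the last dose.
- **That replacement depends only on leaving the study.** Section 5.5 would replace a patient who stays on study but stops crenolanib early for reasons other than toxicity or progression.
- **That the phrase "regardless of amount of study drug administered in a cycle" excuses low exposure.** In Section 5.3.2 it concerns keeping procedures and visits to the study calendar and says nothing about DLT evaluability.
- **That Arm 1 is always less exposed than Arm 2.** Section 5.3.2 has responding patients treated every 4 to 6 weeks. With a next cycle on day 43 and the 72-hour stop, the last crenolanib day is 39, giving 39 − 11 + 1 = 29 to 39 − 5 + 1 = 35 days. No stop is needed before maintenance. The shortfall arises only when cycle 1 ends near day 28.
- **That the window wording is a plain contradiction.** The first cycle of crenolanib treatment can be read as cycle 1, the cycle in which crenolanib is first given. It is ambiguous, and in Arm 1 the two readings start on different days.

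Long non-DLT holds may also be uncommon. The holds required by Table 6.1 are for grade 3 or 4 toxicity, which largely overlaps the DLT definition, and Section 6.2 plans no interruption for myelosuppression in the first 4 weeks. There are later safeguards: the MTD may be refined for delayed or cumulative toxicity, the phase II dose must be deliverable over multiple cycles, toxicity is monitored in cohorts of 4 in phase II, and the sponsor reviews safety as each dose level completes.

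These points limit how often the problem would bite and how far it would go. None supplies an exposure criterion for the escalation count, and none covers the patient held or stopped for sub-DLT toxicity.

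**Conclusion.** The concern holds in this form: no exposure floor is defined for counting a patient as without DLT, two replacement rules conflict, and the DLT window is worded in two ways. Followed exactly, the rules allow under-exposed patients to help clear a dose. In Arm 1, day 28 can be reached with 18 to 24 crenolanib days without any hold, or 15 to 21 with a next cycle on day 29.

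The exposure days follow from the documents. The change in clearing probability does not: it rests on assumed DLT rates, a constant hazard and equal exposure across the six patients. Across the assumed rates of 20% to 40%, moving from 28 to 18 days adds between 15 (81 − 66) and 24 (47 − 23) percentage points to the chance of clearing. The direction is the same at every rate shown. The size in this trial cannot be known from the documents, and a reader should not infer that the MTD will be overstated by a given amount.

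**What to change.** Reconcile the synopsis and Sections 3, 5.1, 5.2, 5.3.1, 5.3.2 and 5.5 into one DLT window and one replacement rule, including how early progression is handled. Specifically:

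1. Count the minimum DLT observation period from the first crenolanib dose in both arms, and keep counting DLTs to the end of cycle 1.
2. Define DLT-evaluable as a patient with a DLT, or one who took at least a pre-stated share (for example 75%) of the planned crenolanib doses in that period. The planned number should allow for the single-dose pharmacokinetic day in Section 8.
3. State in Table 5.1 that a patient moves from pending to without DLT only when evaluable in this sense.
4. Replace other patients for the escalation decision only. Report them separately with the reason for under-dosing, including sub-DLT toxicity, and keep all treated patients in the safety set.

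This is a wording amendment. It costs a few replacement patients and slightly later Arm 1 cohort decisions when cycle 1 ends near day 28. The maximum of 18 per arm is exactly 3 × 6, with no allowance for replacements, so the text should say whether it counts enrolled or DLT-evaluable patients.

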#### **MEC**

Crenolanib TID PO administered daily continuously starting on Day 8 (+3 day window). Crenolanib should be discontinued 3 days (72 hours) before the commencement of the next cycle of chemotherapy.

One induction cycle is defined as the first dose of chemotherapy until response can be assessed and treating physician decides on the follow-up regimen. An induction cycle can be a minimum of 28 days and a maximum of 60 days (extending a cycle over 60 days will require a conversation with the sponsor).

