#### 5. TREATMENT PLAN

#### 5.1. General

Patients will be assigned to treatment arm by physician's choice and according to the availability of slots.

The study will enroll patients with relapsed/refractory AML with FLT3 activating mutations. There will be two parallel two arms. In Arm 1 patients will be treated with standard salvage chemotherapy combined with crenolanib. In Arm 2 patients will receive azacitidine combined with crenolanib. Arms 1 and 2 will enroll simultaneously. For both arms, patients will be treated with crenolanib at a starting dose level of 1 (60 mg TID) as defined in the Table 6.2. De-escalation to dose level 0 (60 mg BID) is possible in the event that dose level 1 is found to be too toxic. The dose escalation will proceed independently in each arm. In arm 1 a cycle of induction or consolidation can last for a minimum of 28 days and a maximum of 60 days (extending a cycle for more than 60 days would require a conversation with the sponsor); maintenance cycles will be defined as 28 days. In arm 2 a cycle is defined as 28 days. The first cycle of treatment (in arm 1 and arm 2 independently) will constitute the dose-limiting toxicity (DLT) evaluation period. Study drug will be taken continuously until one of the criteria for study discontinuation is fulfilled.

For each arm of the study, the first 6 patients will be treated at a dose level of 1(60 mg TID). Patients will be entered sequentially to subsequent dose levels, dose level 2 (80 mg TID) and dose level 3 (100 mg TID) after DLTs have been assessed and it is safe to dose escalate. The Rolling-6 design will be used. The Rolling-6 design aims to shorten the duration of Phase I trials by minimizing the time the trial would be closed to accrual for toxicity monitoring. This is achieved by enrolling anywhere from 2 to 6 patients at a dose level without requiring that the DLT status of the patients already assigned to the same dose level are known.

Dose Escalation/De-Escalation Rules in phase I

The following table enumerates all possible scenarios and describes escalation/de-escalation rules that will be applied during dose-finding, separately in each arm:

Table 5.1. Dose escalation/de-escalation rules for the Rolling-6 design

	Dose	e Escalation/De-	Escalation Rules fo	r the Rolling-6 D	Design
				Decision when	n Next Patient is Enrolled
# Pats Enrolled	# Pats with DLTs	# Pats w/o DLT	# Pats with Toxicity Data Pending	Not at the Highest Dose Level	At the Highest Dose Level

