10. CRITERIA FOR RESPONSE

For AML, response criteria will be modified from the International Working Group for AML [28]. Responders are patients who obtain a CR, CRi, or PR, with or without cytogenetic response, hematologic improvements, and morphologic leukemia-free state. Briefly, criteria are as follows:

(1).	Complete Remission (CR)
	Peripheral blood counts:
	No circulating blasts
	Neutrophil count $\geq 1.0 \times 10^9 / L$
	Platelet count $\geq 100 \text{ x} 10^9 / \text{L}$
	Bone marrow aspirate and biopsy:
	≤5% blasts
	No Auer rods
	No extramedullary leukemia
(2).	Complete Remission with Incomplete Blood Count Recovery (CRi)
	Peripheral blood counts:
	No circulating blasts
	Neutrophil count $<1.0 \times 10^9/L$ , or
	Platelet count $<100 \text{ x} 10^9/\text{L}$
	Bone marrow aspirate and biopsy:
	≤ 5% blasts
	No Auer rods
	No extramedullary leukemia
(3).	Partial Remission (PR)
	50 % reduction in bone marrow blast and to >5% and <20%.
(4).	Morphologic Leukemia-Free State
	Bone marrow: ≤ 5% myeloblasts
(5).	Hematologic Improvement (HI)
Her	natologic response must be described by the number of positively affected cell lines.
	Erythroid response (E) (pretreatment Hgb <11 g/dL)
	Hgb increase by $\ge 1.5 \text{ g/dL}$
	Platelet response (P) (pretreatment platelets $<100 \text{ x} 10^9/\text{L}$ )
	Absolute increase of $\ge 30 \times 10^9 / L$ for patients starting with $> 20 \times 10^9 / L$ platelets
	Increase from $\leq 20 \times 10^9/L$ to $\geq 20 \times 10^9/L$ and by at least $100\%$
	Neutrophil response (N) (pretreatment ANC <1.0 x10  /L)
	At least 100% increase and an absolute increase $> 0.5 \times 10^9/L$
	Blast response (B)
	At least a 50% reduction in blast percentage in peripheral blood (if > 5%) or bone marrow
	For high-risk MDS, response will use the International Working Group criteria [29].

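### In Arm 1, a patient read as CRi can leave the DLT window before the 6-week hematologic DLT can be scored

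*Combined protocol and SAP*

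**What the plan says.** Section 5.1 states: "The first cycle of treatment (in arm 1 and arm 2 independently) will constitute the dose-limiting toxicity (DLT) evaluation period". Sections 5.3.1 and 12.1 likewise tie the DLT to the first cycle. The end of that cycle in Arm 1 is worded in three ways:

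- Sections 5.1 and 5.2.1: "In arm 1 a cycle of induction or consolidation can last for a minimum of 28 days and a maximum of 60 days", with longer cycles needing a conversation with the sponsor. Response plays no part.
- Study Scheme, MEC box: "One induction cycle is defined as the first dose of chemotherapy until response can be assessed and treating physician decides on the follow-up regimen", followed by the same 28 to 60 days.
- Section 5.3.2: "One induction cycle can continue for a minimum of 28 days and a maximum of 60 days from the start of induction chemotherapy", and then "until the start of the second cycle of therapy (reinduction or consolidation) or achievement of CR/CRi/CRp".

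Section 5.3.1 defines the hematologic DLT as grade 3 or worse neutropenia and/or thrombocytopenia with a hypocellular marrow, "lasting for 6 weeks or more after the last dose of therapy in the absence of residual leukemia (i.e., with less than 5% blasts".

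For AML, Section 10 defines CRi by no more than 5% marrow blasts, neutrophils below 1.0 or platelets below 100 x10^9/L, and no circulating blasts, Auer rods or extramedullary leukemia. It sets no requirement for cellularity. Sections 8 and 9 leave on-study marrow timing to institutional standard of care.

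**The concern.** A window that ends at remission can end because of the marrow finding that the hematologic DLT itself requires. That DLT applies only when leukemia has cleared. Clearance with low counts is also CRi, and under Section 5.3.2 CRi ends the cycle. If the 6 weeks are not yet over, the patient leaves the DLT window with the cytopenia unresolved.

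Section 5.3.2 replaces patients only if they are removed before day 28 for reasons other than toxicity. A patient whose cycle closes later is kept and can be counted as without DLT in Table 5.1. The Arm 1 dose decision could then rest on an undercount of a toxicity that the protocol names as dose-limiting. That decision sets the phase II dose, and under Section 12.1 the six patients treated at the MTD are carried into phase II.

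**Working it through.** The plan gives no figure on this point, so there is none to reproduce. The check compares definitions, counts days, and then illustrates the effect on escalation.

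**1. Overlap of the two states.**

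| Criterion | Hematologic DLT (5.3.1, grades from Appendix III) | CRi (Section 10) |
|---|---|---|
| Neutrophils, x10^9/L | below 1.0 | below 1.0 |
| and/or platelets, x10^9/L | below 50 | below 100 |
| Marrow blasts | under 5% | 5% or less |
| Cellularity | hypocellular | not specified |

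Any patient who meets the DLT count and blast criteria meets those of CRi. CRi also requires no circulating blasts, Auer rods or extramedullary leukemia, which a patient without residual leukemia would normally satisfy.

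**2. Earliest day the DLT can be complete, counted from the last chemotherapy dose.** Day 1 is the start of chemotherapy (5.3.2). Last chemotherapy days are from 5.2.1. Earliest day = last chemotherapy day + 42.

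| Regimen | Last chemotherapy day | Earliest DLT day | Days after day 28 | Days left to day 60 |
|---|---|---|---|---|
| Ida/cytarabine, over 60 years | 3 | 45 | 17 | 15 |
| Ida/cytarabine, 60 years or under | 4 | 46 | 18 | 14 |
| FLAG-Ida | 5 | 47 | 19 | 13 |
| MEC | 7 | 49 | 21 | 11 |

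A marrow read as CRi from day 28 to day 44 to 48, depending on regimen, closes the cycle first. With a window that ran to day 60 regardless of response, the event could be scored with 11 to 15 days to spare.

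**3. The same count if crenolanib is part of the last dose.** Crenolanib is given continuously until 72 hours before the next chemotherapy cycle (5.2.1). Completing 42 days by day 60 requires the last crenolanib dose by day 60 - 42 = 18. A last dose on day 25 puts the event at day 25 + 42 = 67, beyond the 60-day limit even without the remission clause.

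**4. Effect on escalation (assumed rates; the documents give none).** A 6-patient level passes with 0 or 1 DLT (5.3.2). With scored DLT probability p per patient, P(pass) = (1-p)^6 + 6p(1-p)^5. If a fraction f of hematologic DLTs is missed and there is no other DLT, p = (true rate) x (1-f).

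| True hematologic DLT rate | f = 0 | f = 0.25 | f = 0.50 | f = 0.75 | f = 1 |
|---|---|---|---|---|---|
| 20% | 0.66 | 0.78 | 0.89 | 0.97 | 1.00 |
| 30% | 0.42 | 0.59 | 0.78 | 0.93 | 1.00 |

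Example at 30% with half missed: p = 0.15, so 0.85^6 + 6(0.15)(0.85^5) = 0.377 + 0.399 = 0.776.

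Full-loss bound with an assumed 10% non-hematologic DLT rate, taken as independent, where p = 1 - 0.9 x (1 - hematologic rate) if all events count: P(pass) is 88.6% if every hematologic event is lost. It is 68.0%, 46.4% and 28.3% if they all count at true rates of 10%, 20% and 30% (p = 0.19, 0.28, 0.37).

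**The case against.** - **Onset reading.** Section 5.3.1 could be read as requiring only that the cytopenia begin in cycle 1, with the 6 weeks confirmed later. On that reading nothing is lost. The reading is possible, but the duration is part of the event's definition and no section says that persistence may be completed after the cycle ends. Two sites could classify the same patient differently.
- **Marrow timing and labelling.** No marrow is fixed at or after day 28. If the first qualifying marrow is read at 6 weeks or later, CRi and the DLT coincide. A hypocellular, blast-free marrow also fits morphologic leukemia-free state in Section 10, which does not end a cycle. This stands, and it leaves the frequency unknown.
- **The 28-day minimum.** It can be read as barring closure before day 28. That is fair, but the 17 to 21 days that follow remain exposed.
- **Other safeguards.** Section 5.1 lets the MTD be refined for late or accumulating toxicity and asks that the phase II dose be deliverable on time over several cycles. Section 5.3.2 makes responders wait for count recovery before further courses, Section 6.2 addresses recovery delayed beyond 6 weeks, and Section 13.2 has the sponsor review safety at each dose level. Prolonged aplasia would therefore not go unseen. None of these puts the event into the Table 5.1 count.
- **Countable rate.** Section 5.3.1 excludes events expected from the chemotherapy, so the true rate of countable events may be below the rates assumed here.

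**Conclusion.** The point holds as a possibility that the text creates: an AML patient in Arm 1 can be read as CRi and leave the DLT window before a named DLT can be met. The partial-loss table shows a material effect on escalation if a quarter to a half of such events were missed. Its rates are assumptions and the full-loss figures are a ceiling. High-risk MDS patients are scored by other response criteria that the protocol does not reproduce, so the overlap is shown for AML only.

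A reader might infer more than the documents support:

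- *That such patients usually leave the window first, or that the Arm 1 MTD would rest almost wholly on non-hematologic events.* Marrow timing and the choice between CRi and leukemia-free state are left open, so no frequency can be given.
- *That Section 5.3.2 contradicts the 28 to 60 days of Section 5.1.* It states the same limits. The conflict is the added remission clause.
- *That responders are watched for a shorter time while non-responders are followed to day 60.* With sponsor and PI agreement, Sections 5.2.3 and 5.3.2 allow patients with active disease to start the next cycle from day 21, so a non-responder's window can close earlier still.
- *That deleting the remission clause is enough.* The Study Scheme wording also ends the cycle around response assessment, and if crenolanib counts as the last dose the 6 weeks can run past day 60.

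**What to change.** Reconcile the Study Scheme and Sections 5.1, 5.2.1, 5.3.1 and 5.3.2 as follows:

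1. State one Arm 1 DLT evaluation window that does not depend on response, and remove the remission clause from the cycle definition as used for DLT.
2. State whether the last dose of therapy means chemotherapy only or includes crenolanib. The documents do not settle this, and this point does not favor either.
3. State whether cytopenia that begins in cycle 1 and completes 6 weeks after the cycle ends counts as a DLT.
4. State that a patient with unresolved cytopenia that could still meet the hematologic DLT is carried in the pending column of Table 5.1.

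The cost is protocol wording and some waiting. Escalation could be delayed by about 2 to 3 weeks counted from the last chemotherapy dose (17 to 21 days past day 28), and by longer if crenolanib counts as the last dose. Under Table 5.1, with six enrolled and no DLT, two or more pending patients suspend accrual. With one DLT already recorded, a single pending patient does.
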